Appendix 3. A Logistic-Normal GLMM for Longitudinal Binary Data and Multiple Imputations

Let Y_{ij} be the binary outcome for participant i ($i = 1, 2, \dots, N$) and post baseline visit j ($j = 1, \dots, 7$) for Weeks 2, 4, 8, 12, 16, 20 and 26. We assume $Y_{ij} = 1$ for a response and $Y_{ij} = 0$ for a non-response. Then we model as

$$P(Y_{ij} = 1 | x_{ij}, u_i) = \frac{e^{\beta' x_{ij} + u_i}}{1 + e^{\beta' x_{ij} + u_i}} \equiv \pi_{ij}(\beta; u_i)$$

Here, β is a vector of unknown parameters corresponding to the vector of fixed effects x_{ij} and u_i is a participant-specific random effect which is assumed to be normally distributed with mean 0 and variance σ^2 . Note that conditional on u_i , Y_{ij} is independent of Y_{ik} , when $j \neq k$.

The full marginal likelihood of the data is then,

$$L(\beta, \sigma^2) = \prod_{i=1}^N \int_{-\infty}^{\infty} \prod_{j=1}^7 \pi_{ij}(\beta; u_i)^{Y_{ij}} (1 - \pi_{ij}(\beta; u_i))^{(1-Y_{ij})} \times N(u_i; 0, \sigma^2) du_i$$

There is no closed analytical form for this likelihood.

For the present study, the primary and key secondary endpoints are evaluated at Week 2, 4 and 16 ($j = 1, 2$) and 5. There are 2 treatment groups, so the model term $\beta' x_{ij}$ when written out looks like,

$$\beta_0 + \sum_{k=1}^2 \beta_{1k} \times 1_{(T_i=k)} + \beta_{2j} + \sum_{k=1}^2 \beta_{3jk} \times 1_{(T_i=k)}$$

Here, T_i represents treatment for participant i where $T_i = 1$ if the participant is randomized to abrocitinib, and $T_i = 2$ if the participant is randomized to dupilumab. The third term β_{2j} in the expression is the effect for visit j and the fourth term in the expression is the interaction effect between treatment and visit. With an overall intercept term, the model is over-parameterized as written and so to fit the model, some restrictions on β are required. The default option in many standard statistical software is to assume $\beta_{12} = 0, \beta_{27} = 0$, thereby interpreting β_{11} as the difference in treatment effect relative to $T = 2$ and β_{2j} as the difference in visit effect relative to $V = 7$. Consequently, $\beta_{3jk} = 0$ when $j = 7$ or $k = 2$. So, for example, for a participant taking abrocitinib at Week 16, the expression would be $\beta_0 + \beta_{11} + \beta_{25} + \beta_{351}$. For a participant taking dupilumab at Week 4, the expression would be $\beta_0 + \beta_{22}$.

The saturated logit-normal GLMM as described above will be used as the imputation model. Estimation of the model parameters will be performed under the Bayesian framework using Markov Chain Monte Carlo (MCMC) methods. We assign a non-informative prior for each component of β to be independent and identically distributed as $\sim N(0, 10000)$ and assign a weakly informative prior for σ^2 as an Inverse-Gamma distribution with shape=1 and scale=1. With this prior distribution, the 90th percentile for σ^2 is approximately 9.

Let $\beta^b, u_i^b, b = 1, 2, \dots, B$ be a sample from the posterior distribution. A single imputation $\widetilde{Y}_{i,j}^b$ of missing Y_{ij} is based on the posterior predictive distribution of the response probabilities estimated from the GLMM. For example, if participant i is randomized to abrocitinib ($T_i = 1$), then at Week 16 ($V = 5$),

$$\text{logit}(\pi_{i,1,5}^b) = \text{logit}\left(P\left(\widetilde{Y}_{i,5}^b = 1 \mid T_i = 1, V = 5\right)\right) = \beta_0^b + \beta_{11}^b + \beta_{25}^b + \beta_{351}^b + u_i^b.$$

If participant i is randomized to dupilumab ($T_i = 2$), then at Week 16 ($V = 5$),

$$\text{logit}(\pi_{i,2,5}^b) = \text{logit}\left(P\left(\widetilde{Y}_{i,4}^b = 1 \mid T_i = 2, V = 5\right)\right) = \beta_0^b + \beta_{25}^b + u_i^b.$$

We then sample the single imputed value $\widetilde{Y}_{i,j}^b$ from a Bernoulli distribution with probability of success $\pi_{i,T_i,5}^b$.

Analysis of an imputed data set will produce an estimate as well as standard error of the treatment difference using CMH and normal approximation ([Section 5.2.1](#)). This is repeated for B (typically, $B=500$) times to generate B complete imputed data sets and these B sets of estimates are combined using the Rubin's Method (Rubin, 1987).

Appendix 4. Expected Number of Injections

Expected Number of Injections (Cumulative) will be based on Last Injection Date relative to Day 1/Baseline, using the following table:

Injection Schedule	Target Day	Window	Expected Number of Injections (Cumulative)
Baseline	Day 1	Days 1 to 7	2
Week 2	Day 15	Days 8 to 21	3
Week 4	Day 29	Days 22 to 35	4
Week 6	Day 43	Days 36 to 49	5
Week 8	Day 57	Days 50 to 63	6
Week 10	Day 71	Days 64 to 77	7
Week 12	Day 85	Days 78 to 91	8
Week 14	Day 99	Days 92 to 105	9
Week 16	Day 113	Days 106 to 119	10
Week 18	Day 127	Days 120 to 133	11
Week 20	Day 141	Days 134 to 147	12
Week 22	Day 155	Days 148 to 161	13
Week 24	Day 169	Days 162 to -	14

Eg, if a subject receives his/her last injection on Day 76, the Expected Number of Injections (Cumulative) should be 7.

Appendix 5. Eczema Area and Severity Index (EASI)

The EASI quantifies the severity of a participant's atopic dermatitis based on both severity of lesion clinical signs and the percent of BSA affected. EASI is a composite scoring by the atopic dermatitis clinical evaluator of the degree of erythema, induration/papulation, excoriation, and lichenification (each scored separately) for each of four body regions, with adjustment for the percent of BSA involved for each body region and for the proportion of the body region to the whole body.

Lesion Severity by Clinical Signs: The basic characteristics of atopic dermatitis lesions-erythema, induration/papulation, excoriation, and lichenification-provide a means for assessing the severity of lesions. Assessment of these four main clinical signs is performed separately for four body regions: head and neck, upper limbs, trunk (including axillae and groin) and lower limbs (including buttocks). Average erythema, induration/papulation, excoriation, and lichenification are scored for each body region according to a 4-point scale: 0=absent; 1=mild; 2=moderate; 3=severe. Morphologic descriptors for each clinical sign severity score are shown in the table below.

Clinical Sign Severity Scoring Criteria for the EASI

Score		Description
Erythema (E)		
0	Absent	None; may have residual discoloration (post-inflammatory hyperpigmentation and/or hypopigmentation).
1	Mild	Light pink to light red
2	Moderate	Red
3	Severe	Deep, dark red
Induration/Papulation (I)		
0	Absent	None
1	Mild	Barely palpable to slight, but definite hard thickened skin and/or papules
2	Moderate	Easily palpable moderate hard thickened skin and/or papules
3	Severe	Severe hard thickened skin and/or papules
Excoriation (Ex)		
0	Absent	None
1	Mild	Slight, but definite linear or picked scratch marks or penetrating surface injury
2	Moderate	Moderate linear or picked scratch marks or penetrating surface injury
3	Severe	Severe linear or picked scratch marks or penetrating surface injury
Lichenification (L)		
0	Absent	None
1	Mild	Barely perceptible to slight, but definite thickened skin, fine skin markings, and lichenoid scale

Score		Description
2	Moderate	Moderate thickened skin, coarse skin markings, and coarse lichenoid scale
3	Severe	Severe thickened skin with very coarse skin markings and lichenoid scale

%BSA with Atopic Dermatitis: The number of handprints of skin afflicted with atopic dermatitis in a body region can be used to determine the extent (%) to which a body region is involved with atopic dermatitis (see table below). When measuring, the handprint unit refers to the size of each individual participant’s hand with fingers in a closed position.

Handprint Determination of %BSA

Body Region	Total Number of Handprints in Body Region*	Surface Area of Body Region Equivalent of One Handprint*
Head and Neck	10	10%
Upper Limbs	20	5%
Trunk (including axillae and groin/genitals)	30	3.33%
Lower Limbs (including buttocks)	40	2.5%

*Handprint refers to the hand size of each individual participant.

EASI Area Score Criteria

Percent BSA with Atopic Dermatitis in a Body Region	Area Score
0%	0
>0 - <10%	1
10 - <30%	2
30 - <50%	3
50 - <70%	4
70 - <90%	5
90 - 100%	6

Body Region Weighting: Each body region is weighted according to its approximate percentage of the whole body (see table below).

EASI Body Region Weighting

Body Region	Body Region Weighting
Head and Neck	0.1
Upper Limbs	0.2
Trunk (including axillae and groin/genitals)	0.3
Lower Limbs (including buttocks)	0.4

In each body region, the sum of the Clinical Signs Severity Scores for erythema, induration/papulation, excoriation, and lichenification is multiplied by the Area Score and by the Body Region Weighting to provide a body region value, which is then summed across all four body regions resulting in an EASI score as described in Equation below.

$$EASI = 0.1Ah(Eh+Ih+Exh+Lh) + 0.2Au(Eu+Iu+ExU+Lu) + 0.3At(Et+It+Ext+Lt) + 0.4Al(EI+II+ExI+LI)$$

A = Area Score; E = erythema; I = induration/papulation; Ex = excoriation; L = lichenification; h = head and neck; u = upper limbs; t = trunk; l = lower limbs

The EASI score can vary in increments of 0.1 and range from 0.0 to 72.0, with higher scores representing greater severity of atopic dermatitis.

Appendix 6. Peak Pruritus Numerical Rating Scale (PP-NRS)

The severity of itch (pruritus) due to AD will be assessed using the PP-NRS, a validated horizontal NRS. Participants will be asked to assess their worst itching due to AD over the past 24 hours on an NRS anchored by the terms “no itch” (0) and “worst itch imaginable” (10). This item will be administered to all participants. Participants will enter the PP-NRS assessment into an eDiary on a daily basis from the Screening visit through the Week 30 visit.

Appendix 7. Abbreviations

Abbreviation	Term
AD	atopic dermatitis
AE	adverse event
ALT	alanine aminotransferase
ANCOVA	Analysis of Covariance
ALT	alanine aminotransferase
AST	aspartate aminotransferase
BSA	body surface area
CaPS	CDISC and Pfizer Standards
CDISC	Clinical Data Interchange Standards Consortium
CI	Confidence Interval
CMH	Cochran-Mantel-Haenszel
CO ₂	carbon dioxide
CsA	cyclosporine A
CSR	clinical study report
C-SSRS	Columbia Suicide Severity Rating Scale
DLQI	Dermatology Life Quality Index
DMC	data monitoring committee
EASI	Eczema Area and Severity Index
EASI-90	Response based on achieving $\geq 90\%$ improvement from baseline in Eczema Area and Severity Index
EASI-75	Response based on achieving $\geq 75\%$ improvement from baseline in Eczema Area and Severity Index
ECG	electrocardiogram
ED	early discontinuation
eDiary	electronic diary
E-DMC	external data monitoring committee
EOS	End of Study
EOT	End of Treatment
EQ-5D-5L	EuroQol Quality of Life 5-Dimension 5-Level Scale
EU	European Union
FAS	full analysis set
FDA	Food and Drug Administration
GGT	gamma-glutamyl transferase
GLMM	Generalized Linear Mixed Model
HADS	Hospital Anxiety and Depression Scale
HCRU	Health Care Resource Utilization
hsCRP	high-sensitivity C-reactive protein
ID	identification

Abbreviation	Term
IGA	Investigator's Global Assessment
LDH	lactate dehydrogenase
LDL	low-density lipoprotein
LFT	liver function test
LLQ	lower limit of quantification
LSM	Least squares mean
LTE	long-term extension
MAR	missing at random
MCAR	Missing completely at random
MCH	mean corpuscular hemoglobin
MCHC	mean corpuscular hemoglobin concentration
MCMC	Markov Chain Monte Carlo
MCV	mean corpuscular volume
MedDRA	Medical Dictionary for Regulatory Activities
MMRM	mixed-effect model with repeated measures
MNAR	missing not at random
MOS	medical outcomes study
MTX	methotrexate
N/A	not applicable
NB-UVB	narrowband ultraviolet B light
NI	non-inferiority
NRS	numerical rating scale
PCD	primary completion date
PDE4	phosphodiesterase 4
PFS	prefilled syringe
PHQ-8	Patient Health Questionnaire - 8 items
PK	Pharmacokinetic(s)
POEM	Patient-Oriented Eczema Measure
PPAS	per-protocol analysis set
PP-NRS	Peak Pruritus Numerical Rating Scale
PP-NRS4	Response based on achieving at least a 4-point improvement in the severity of Peak Pruritus Numerical Rating Scale
PRO	patient reported outcome
PSAAD	Pruritus and Symptoms Assessment for Atopic Dermatitis
Q2W	every two weeks
QD	once daily
QoL	quality of life
RBC	red blood cell
REML	restricted maximum likelihood
SAE	serious adverse event
SAP	statistical analysis plan

Abbreviation	Term
SCORAD	SCORing atopic dermatitis
SoA	schedule of activities
SOC	system organ class
SP-NRS	Skin Pain Numerical Rating Scale
TB	tuberculosis
TCI	topical calcineurin inhibitors
TCS	topical corticosteroids
TEAE	Treatment-Emergent Adverse Event
US	United States
UVA	ultraviolet A light
UVB	ultraviolet B light
WBC	white blood cell

Appendix 8. Additional Analyses (Not for CSR Purpose)

The following analyses will be produced at the same time with CSR tables, but will be used for publication or internal reporting purpose, and generally not to be reported in the CSR.

Appendix 8.1. Definitions

Appendix 8.1.1. PP-NRS Weekly Average

PP-NRS is recorded every day throughout the study. PP-NRS (Weekly Average) is defined as the simple average of observed measures within a week. If two or more values are collected on the same day, the last measurement of the day will be used for calculating the average. There should be at least 4 days of observed PP-NRS within a specified week to calculate the average; otherwise the weekly average is set to missing

$$\text{Baseline} = \text{avg}(\text{PP-NRS Day } -6 \sim \text{Day } -1, \text{ Day } 1)$$

$$\text{Week } 1 = \text{avg}(\text{PP-NRS Day } 2 \sim \text{Day } 8)$$

$$\text{Week } 2 = \text{avg}(\text{PP-NRS Day } 9 \sim \text{Day } 15)$$

...

$$\text{Week } [k] = \text{avg}(\text{PP-NRS Day } [7k-5] \sim \text{Day } [7k+1]), 2 < k < 26$$

...

$$\text{Week } 26 = \text{avg}(\text{PP-NRS Day } 177 \sim \text{Day } 183)$$

Appendix 8.1.2. EASI by Body Region

$$\text{EASI head and neck} = .1A_h(E_h + I_h + Ex_h + L_h)$$

$$\text{EASI upper limbs} = .2A_u(E_u + I_u + Ex_u + L_u)$$

$$\text{EASI trunk} = .3A_t(E_t + I_t + Ex_t + L_t)$$

$$\text{EASI lower limbs} = .4A_l(E_l + I_l + Ex_l + L_l)$$

A = Area Score; E = erythema; I = induration/papulation; Ex = excoriation; L = lichenification; h = head and neck; u = upper limbs; t = trunk; l = lower limbs

Appendix 8.1.3. EASI And %BSA excluding scalp, palms and soles of feet

At each scheduled visit, the following region of AD involvement by handprint will be entered into CRF: Scalp Area Handprint (SAH; max = 3.0), Hand Ventral Right (HVR; max = 1.0), Hand Ventral Left (HVL; max = 1.0), Foot Ventral Right (FVR; max =2.0) and Foot

Ventral Right (FVR; max =2.0). New %BSA will be derived by subtracting those hand prints from corresponding original EASI % BSA.

Handprint Determination of %BSA excluding scalp, palms and soles of feet

Body Region	Derivation	Total Number of Handprints in Body Region	Surface Area of Body Region Equivalent of One Handprint*
Head and Neck excluding Scalp	Head and Neck - SAH	7	10%
Upper Limbs excluding Palms	Upper Limbs – HVR - HVL	18	5%
Trunk (including axillae and groin/genitals)	Trunk (including axillae and groin/genitals)	30	3.33%
Lower Limbs (including buttocks) excluding soles	Lower Limbs (including buttocks) excluding soles – FVR - FVR	36	2.50%

EASI excluding scalp, palms and soles of feet will be derived using the same method specified in [Appendix 5](#) but with the %BSA excluding scalp, palms and soles of feet.

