Appendix 8.2.2. Binary endpoints

- Endpoints:
 - Weeks 2, 4, 8, 12, 16, 20 and 26 EASI-100, SCORAD75 (75% improvement from baseline), SCORAD90 (90% improvement from baseline), IGA of “Clear” Response
 - Weeks 2, 4, 8, 12, 16, 20 and 26 %BSA < 5%, PP-NRS <2, SCORAD (VAS) of Sleep Loss <2 Response
 - Weeks 1 ~ 26 PP-NRS4 (based on weekly average)
 - Weeks 2, 4, 8, 12, 16, 20 and 26 EASI-75, EASI-90, %BSA < 5% Response based on EASI (excluding scalp, palms and soles of feet) and %BSA (excluding scalp, palms and soles of feet)
 - Weeks 2, 12, 16, 20 and 26 DLQI < 2 Response
 - Weeks 12, 16 and 26 HADS Anxiety <8 Points, HADS Depression <8 Points Response
 - Weeks 12, 16 and 26 POEM \geq 4 points improvement from baseline, POEM <3 Response
 - Weeks 2, 12, 16, 20 and 26 Response based on achieving at least a 4-point improvement in the Skin Pain NRS
 - Baseline, Weeks 12, 16 and 26 Response based on achieving MOS-Sleep Scale Optimal Hours Slept Score of 1.
- Estimand strategy: Estimand 1, composite estimand.

- Analysis set: FAS (Section 4).
 - Analyses for binary endpoints that are defined based on reaching a threshold of absolute level (eg, PP-NRS <2) or change from baseline (eg, POEM ≥ 4 points improvement from baseline) will also require baseline value to be equal to or greater than that threshold (eg, for PP-NRS <2 , the baseline value needs to be ≥ 2 ; for POEM ≥ 4 points improvement, the baseline value needs to be ≥ 4 points) to be included in the analysis.
- Analysis methodology: CMH and normal approximation in Section 5.2.1.

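### SAP Appendix 8.1.3 subtracts the right sole twice and pairs reduced handprint totals with whole-region percentages, so the modified EASI and %BSA are mis-specified as written

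*SAP*

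**What the plan says.** SAP Appendix 8.1.3 gives this rule: "New %BSA will be derived by subtracting those hand prints from corresponding original EASI % BSA". The sites to remove are listed as "Scalp Area Handprint (SAH; max = 3.0), Hand Ventral Right (HVR; max = 1.0), Hand Ventral Left (HVL; max = 1.0"), followed by two foot entries. Both foot entries are named as the right foot; the second ends "Ventral Right (FVR; max =2.0").

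The table then gives, for each region, a derivation, a handprint total and the percentage of the region that one handprint represents:

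- head and neck: "Head and Neck - SAH 7 10"%;
- upper limbs: "Upper Limbs – HVR - HVL 18 5"%;
- trunk: 30 handprints at 3.33%, unchanged;
- lower limbs: "Lower Limbs (including buttocks) excluding soles – FVR - FVR", 36 handprints at 2.50%.

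The modified EASI is then computed by the Appendix 5 method. It feeds EASI-75 and EASI-90, and the modified %BSA feeds a below-5% response (Appendix 8.2.2: "BSA < 5% Response based on EASI (excluding scalp, palms and soles of feet")). Both feed percent change by MMRM (Appendix 8.2.3), and the modified EASI also enters a summary of original minus modified EASI (Appendix 8.2.1). Appendix 8 outputs "will be used for publication or internal reporting purpose" and are generally outside the CSR.

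**The concern.** The two defects are separate.

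First, the palms have a right and a left variable, but the soles have the right one twice. A programmer who follows the table leaves left-sole disease in the score and removes right-sole disease twice. The lower-limb row also starts from a quantity whose label says that the soles are already out.

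Second, the handprint totals were reduced but the percentages were not. A column that gives the share of the region per handprint should multiply by the row total to 100%. Here it gives 7 × 10 = 70%, 18 × 5 = 90% and 36 × 2.5 = 90%. These percentages select the EASI area score, so the modified EASI depends on which half of the table is believed. Two programmers could reasonably produce different scores for the same participant, and some of the results may be published.

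**Working it through.** **Inputs.** SAP Appendix 5: whole-region handprints 10, 20, 30, 40; percentages 10, 5, 3.33, 2.5; area-score cut-points 10, 30, 50, 70, 90%; weights 0.1, 0.2, 0.3, 0.4; four signs scored 0 to 3, so at most 12 per region. SAP Appendix 8.1.3: maxima removed are scalp 3, palms 1 + 1, and two sole entries of 2. Protocol Section 8.1.2.1: total %BSA is the sum of handprints over the four regions.

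**1. Reproducing the printed figures.** Appendix 5 is consistent: 100/10 = 10, 100/20 = 5, 100/30 = 3.33, 100/40 = 2.5. The reduced totals also reproduce: 10 - 3 = 7, 20 - 2 = 18, 40 - (2 + 2) = 36. The reduced-region percentages do not: 100/7 = 14.29 (printed 10), 100/18 = 5.56 (printed 5), 100/36 = 2.78 (printed 2.50). Only the unchanged trunk row agrees. The printed values equal 100/10, 100/20 and 100/40, the Appendix 5 figures.

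**2. Sole term.** Let LL be the whole lower-limb count, R and L the sole handprints (0 to 2 each).

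- As printed: LL - 2R.
- Both soles once: LL - R - L.
- Error: (LL - 2R) - (LL - R - L) = L - R, from -2 to +2 handprints, and zero when the soles are equally involved.

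This is up to 2 points of total %BSA, or 2 × 2.5 = 5 percentage points of the lower limbs at the printed percentage. If the only lower-limb disease is a fully involved right sole, the printed rule gives 2 - 4 = -2 handprints.

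**3. Area scores.** Handprints needed to reach a score = cut-point / percentage per handprint.

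| Region | Scores 2, 3, 4, 5, 6 as printed | Scores 2, 3, 4, 5, 6 matched to the reduced total |
|---|---|---|
| Head and neck (7) | 1, 3, 5, 7, 9 (9 cannot be reached) | 0.7, 2.1, 3.5, 4.9, 6.3 |
| Upper limbs (18) | 2, 6, 10, 14, 18 | 1.8, 5.4, 9, 12.6, 16.2 |
| Lower limbs (36) | 4, 12, 20, 28, 36 | 3.6, 10.8, 18, 25.2, 32.4 |

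A count from the right-hand value up to, but not including, the left-hand value scores lower as printed. In half-handprint steps:

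- head and neck: 2.5 and 3.5 to 7, so 9 of 14;
- upper limbs: 5.5, 9 to 9.5, 13 to 13.5, 16.5 to 17.5, so 1 + 2 + 2 + 3 = 8 of 36;
- lower limbs: 11 to 11.5, 18 to 19.5, 25.5 to 27.5, 32.5 to 35.5, so 2 + 4 + 5 + 7 = 18 of 72.

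The shortfall is one category, except at 6.5 head and neck handprints (65% scores 4; 92.9% scores 6).

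**4. Maximum EASI as printed.** Full involvement gives 70% (score 5), 90% (6), 100% (6) and 90% (6). So 0.1×12×5 + 0.2×12×6 + 0.3×12×6 + 0.4×12×6 = 6 + 14.4 + 21.6 + 28.8 = 70.8, against 72.0.

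**5. Total %BSA.** A sum of handprints (maximum 7 + 18 + 30 + 36 = 91) does not use the percentage per handprint. The scaling defect therefore leaves it, and the below-5% response, unchanged.

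**6. Responder status.** The documents give no distribution of involvement, so only an illustration is possible. One simulation with assumed regional involvement and severity compared printed with matched percentages. EASI-75 went from 81.2% to 82.9% and EASI-90 from 12.5% to 13.7%, with 4.9% and 3.3% of participants reclassified. Individuals moved both ways. One went from 17.8 at baseline and 2.0 at follow-up (88.8% improvement) to 20.6 and 2.0 (90.3%). Another went from 28.5 and 2.7 (90.5%) to 28.5 and 3.0 (89.5%).

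**The case against.** The best defence of the percentages is that whole-region denominators were kept on purpose: subtract the excluded handprints, count those sites as clear, and apply Appendix 5 with its weights. On that reading 70.8 is simply the maximum, and the step counts compare two conventions.

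Rescaling also has a cost. Take 4 head and neck handprints and no scalp disease. The original EASI uses 40%, score 3; the rescaled version uses 57.1%, score 4. The modified EASI then exceeds the original although nothing was removed, which disturbs the difference summary in Appendix 8.2.1. Rescaling also leaves the weights at 0.1, 0.2, 0.3 and 0.4 although the regions are now 7, 18, 30 and 36 of 91.

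This stands in part. The convention is possible, but the SAP does not state it, and the reduced row names, totals and column heading contradict it. The table needs a change either way.

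On the soles, the repeated name is most likely a slip: there are two entries of maximum 2.0, and 36 = 40 - 2 - 2. That stands as to intent. The printed derivation is still wrong if followed.

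It is also fair that fully involved upper and lower limbs, at 90%, still score 6. Only head and neck falls short at full involvement.

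**Conclusion.** Appendix 8.1.3 is wrong as written on both counts, and the consequences are limited.

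The sole term, if coded literally, shifts the lower-limb count by -2 to +2 handprints and can affect both the modified %BSA and the modified EASI. The percentage mismatch affects only the modified EASI, through area scores that are lower at 9 of 14, 8 of 36 and 18 of 72 half-handprint steps. Those counts take percentages matched to the reduced totals as the reference.

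A reader might infer more than the documents support:

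- That the scaling also corrupts %BSA or the below-5% response. It does not; total %BSA is a sum of handprints.
- That the responder rates are wrong. A response changes only if an area score crosses a cut-point and the percent improvement then crosses 75% or 90%. The size is unknown; the simulated figures rest on assumed inputs and do not estimate the effect in this trial.
- That one arm is favoured. The same derivation applies to both arms, and nothing in the documents shows a between-arm bias.
- That the main results are at risk. EASI-90 at Weeks 4 and 16 uses Appendix 5, which is internally consistent, and PP-NRS4 at Week 2 does not use EASI.

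**What to change.** 1. Define a left-sole variable (FVL, maximum 2.0) in the list of collected items. Derive the lower-limb count as the whole lower-limb count minus FVR minus FVL, and remove the label that implies the soles are already out of the starting term. Confirm that the second foot field on the CRF is the left foot; the CRF is not among the documents reviewed.
2. Choose one denominator and make the table agree with it:
   - Reduced regions: 14.29%, 5.56%, 3.33% and 2.78% per handprint for totals of 7, 18, 30 and 36. Add a note that the modified EASI can then exceed the original when no excluded site is involved, so that the difference summary in Appendix 8.2.1 is read accordingly.
   - Whole regions: keep 10%, 5%, 3.33% and 2.5%, restore totals of 10, 20, 30 and 40, and state that excluded sites count as clear.

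The cost is a correction to one SAP table and its introductory sentence, plus a small programming change. If the second foot field is the left foot, no new data are needed.
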